	N	Mean	Median	Standard deviation	IQR	Min - Max
If yes, estimate percentage	XX	XX.X	XX.X	XX.X	xx.x – xxx.x	xx.x – xxx.x
Measurement of common femoral artery (mm)	xx	XX.X	XX.X	x.x	xx.x – xx.x	xx.x – xx.x

DOC-DP2-81 Rev 01

Table 13. Device and deployment details

	N	Mean	Median	Standard deviation	IQR	Min - Max
Procedure time (minutes)	XX	XXX.X	XXX.X	XX.X	xxx.x – xxx.x	xxx.x – xxx.x
Angle of device during deployment (°)						
Time taken to deploy the device from introduction into the	XX	XX.X	XX.X	X.X	xx.x - xx.x	xx.x - xx.x
introducer sheath to procedural sheath and device						
removal (minutes)						
Time from the PerQseal® device and introducer sheath	XX	XX.X	XX.X	X.X	XX.X - XX.X	xx.x - xx.x
removal to haemostasis for the access site arteriotomy						
(minutes)						
	% (n/N)					
Device malfunction during use	xx.x (xx/xx)					
Bleeding						
None	xx.x (xx/xx)					
Ooze	xx.x (xx/xx)					
Brisk	xx.x (xx/xx)					
Pulsatile	xx.x (xx/xx)					

DOC-DP2-81 Rev 01

Table 14. Post-procedural angiogram of femoral vasculature

	% (n/N)					
Evidence of leakage from	xx.x (xx/xx)					
arteriotomy						
Evidence of stenosis of artery	xx.x (xx/xx)					
	N	Mean	Median	Standard	IQR	Min - Max
				deviation		
If yes, estimate percentage	XX	XX.X	XX.X	XX.X	xx.x – xxx.x	xx.x – xxx.x

DOC-DP2-81 Rev 01

Table 15. Pre-discharge examination

	N	Mean	Median	Standard deviation	IQR	Min - Max
Time to ambulation (hours post-procedure)	XX	XXX.X	XXX.X	XX.X	xxx.x - xxx.x	xxx.x – xxx.x
Time to actual discharge (hours post-procedure)	xx	XXX.X	XXX.X	XX.X	xxx.x - xxx.x	xxx.x - xxx.x

DOC-DP2-81 Rev 01

Table 16. Groin condition

		Immediate p	ost-	30 min pos	st-	1 hours po	ost-	Pre-disch	arge	1 month		3 month	
		procedure		procedure		procedure	procedure						
		Left leg	Right leg	Left leg	Right leg	Left leg	Right leg	Left leg	Right leg	Left leg	Right leg	Left leg	Right leg
Ipsilateral groin	Normal - % (n/N)	xx.x (xx/xx)	xx.x (xx/xx)	XX.X									
condition	, ,			(xx/xx)									
	Haematoma - %	xx.x (xx/xx)	xx.x (xx/xx)	xx.x (xx/xx)									
	(n/N) Bleeding - % (n/N)	xx.x (xx/xx)	xx.x (xx/xx)	XX.X									
	5 , ,			(xx/xx)									
	Ecchymosis - % (n/N)	xx.x (xx/xx)	xx.x (xx/xx)	xx.x (xx/xx)									
	Other - % (n/N)	xx.x (xx/xx)	xx.x (xx/xx)	xx.x (xx/xx)									

Table 17. ABI

	Baseline		3 Month	
	Left	Right	Left	Right
N	XX	XX	XX	XX
Mean	X.XX	X.XX	X.XX	X.XX
Median	X.XX	X.XX	X.XX	X.XX
Standard	X.XX	X.XX	X.XX	X.XX
deviation				
IQR	X.XX - X.XX	X.XX - X.XX	x.xx - x.xx	X.XX - X.XX
Min	X.XX	X.XX	X.XX	X.XX
Max	X.XX	X.XX	X.XX	x.xx

Table 18. Lower extremity pulses (palpate)

		Pre-		Imme	diate	30 mi	n	1 hou	r post-	Pre-		1 mor	nth	3 mor	nth
		proce	dure	post-		post-		proce	dure	disch	arge				
				proce	dure	proce	dure								
		Left	Rig	Left	Rig	Left	Rig	Left	Rig	Left	Rig	Left	Rig	Left	Rig
		leg	ht	leg	ht	leg	ht	leg	ht	leg	ht	leg	ht	leg	ht
			leg		leg		leg		leg		leg		leg		leg
Dorsa	Strong	XX.X	XX.X	XX.X	XX.X	XX.X	XX.X	XX.X	XX.X	XX.X	XX.X	XX.X	XX.X	XX.X	XX.X
lis	- %	(xx/	(xx/	(xx/	(xx/	(xx/	(xx/	(xx/	(xx/	(xx/	(xx/	(xx/	(xx/	(xx/	(xx/
pedis	(n/N)	xx)	xx)	xx)	xx)	xx)	xx)	xx)	xx)	xx)	xx)	xx)	xx)	xx)	xx)
	Normal	XX.X	XX.X	XX.X	XX.X	XX.X	XX.X	XX.X	XX.X	XX.X	XX.X	XX.X	XX.X	XX.X	XX.X
	- %	(xx/	(xx/	(xx/	(xx/	(xx/	(xx/	(xx/	(xx/	(xx/	(xx/	(xx/	(xx/	(xx/	(xx/
	(n/N)	xx)	xx)	xx)	xx)	xx)	xx)	xx)	xx)	xx)	xx)	xx)	xx)	xx)	xx)
	Diminis	XX.X	XX.X	XX.X	XX.X	XX.X	XX.X	XX.X	XX.X	XX.X	XX.X	XX.X	XX.X	XX.X	XX.X
	hed - %	(xx/	(xx/	(xx/	(xx/	(xx/	(xx/	(xx/	(xx/	(xx/	(xx/	(xx/	(xx/	(xx/	(xx/
	(n/N)	xx)	xx)	xx)	xx)	xx)	xx)	xx)	xx)	xx)	xx)	xx)	xx)	xx)	xx)
	Absent	XX.X	XX.X	XX.X	XX.X	XX.X	XX.X	XX.X	XX.X	XX.X	XX.X	XX.X	XX.X	XX.X	XX.X
	- %	(xx/	(xx/	(xx/	(xx/	(xx/	(xx/	(xx/	(xx/	(xx/	(xx/	(xx/	(xx/	(xx/	(xx/
	(n/N)	xx)	xx)	xx)	xx)	xx)	xx)	xx)	xx)	xx)	xx)	xx)	xx)	xx)	xx)
Poste	Strong	XX.X	XX.X	XX.X	XX.X	XX.X	XX.X	XX.X	XX.X	XX.X	XX.X	XX.X	XX.X	XX.X	XX.X
rior	- %	(xx/	(xx/	(xx/	(xx/	(xx/	(xx/	(xx/	(xx/	(xx/	(xx/	(xx/	(xx/	(xx/	(xx/
tibial	(n/N)	xx)	xx)	xx)	xx)	xx)	xx)	xx)	xx)	xx)	xx)	xx)	xx)	xx)	xx)
	Normal	XX.X	XX.X	XX.X	XX.X	XX.X	XX.X	XX.X	XX.X	XX.X	XX.X	XX.X	XX.X	XX.X	XX.X
	- %	(xx/	(xx/	(xx/	(xx/	(xx/	(xx/	(xx/	(xx/	(xx/	(xx/	(xx/	(xx/	(xx/	(xx/
	(n/N)	xx)	xx)	xx)	xx)	xx)	xx)	xx)	xx)	xx)	xx)	xx)	xx)	xx)	xx)
	Diminis	XX.X	XX.X	XX.X	XX.X	XX.X	XX.X	XX.X	XX.X	XX.X	XX.X	XX.X	XX.X	XX.X	XX.X
	hed - %	(xx/	(xx/	(xx/	(xx/	(xx/	(xx/	(xx/	(xx/	(xx/	(xx/	(xx/	(xx/	(xx/	(xx/
	(n/N)	xx)	xx)	xx)	xx)	xx)	xx)	xx)	xx)	xx)	xx)	xx)	xx)	xx)	xx)
	Absent	xx.x	XX.X	xx.x	XX.X	xx.x	XX.X	XX.X	xx.x	XX.X	XX.X	xx.x	xx.x	XX.X	XX.X
	- %	(xx/	(xx/	(xx/	(xx/	(xx/	(xx/	(xx/	(xx/	(xx/	(xx/	(xx/	(xx/	(xx/	(xx/
	(n/N)	xx)	xx)	xx)	xx)	xx)	xx)	xx)	xx)	xx)	xx)	xx)	xx)	xx)	xx)

Table 19. 3 Month Duplex ultrasonography

		At a point estimated to be the punctur
		site
	N	xx
	Mean	XX.X
	Median	XX.X
Femoral artery diameter – mediolateral plane (mm)	SD	XX.X
	IQR	xx.x - xxx.x
	Min	xx.x
	Max	xxx.x
	N	xx
	Mean	xx.x
Femoral artery diameter – anteroposterior plane (mm)	Median	xx.x
remoral artery diameter – anteroposterior plane (mm)	SD	xx.x
	IQR	xx.x - xxx.x
	Min	XX.X
	Max	xxx.x
	N	xx
	Mean	xx.x
	Median	xx.x
Blood velocity (cm/s)	SD	xx.x
	IQR	xx.x - xxx.x
	Min	xx.x
	Max	xxx.x
	Yes	xx.x (xx/xx)
Evidence of stenosis of femoral artery	No	xx.x (xx/xx)
	Undetermined	xx.x (xx/xx)
	N	xx
	Mean	xx.x
	Median	xx.x
f yes, estimate of percentage of stenosis of femoral	SD	xx.x
ırtery	IQR	xx.x - xxx.x
	Min	xx.x
	Max	xxx.x
	Medial - % (n/N)	xx.x (xx/xx)
	Lateral - % (n/N)	xx.x (xx/xx)
f yes, location of stenosis of femoral artery	Anterior - % (n/N)	xx.x (xx/xx)
	Posterior - % (n/N)	xx.x (xx/xx)
	Yes - % (n/N)	xx.x (xx/xx)
	No - % (n/N)	xx.x (xx/xx)
Evidence of turbulent flow	Undetermined - %	xx.x (xx/xx)
	(n/N)	
	Yes - % (n/N)	xx.x (xx/xx)
	No - % (n/N)	xx.x (xx/xx)
Evidence of access site related haematoma	Undetermined - %	xx.x (xx/xx)
	(n/N)	

Confidential & proprietary information, not to be reproduced or made available to third parties without prior consent from Vivasure Medical Ltd and not to be used in any unauthorised way.

	Mean	XX.X
	Median	XX.X
Managed and a second	SD	XX.X
If yes, size x-axis	IQR	xx.x - xxx.x
	Min	XX.X
	Max	XXX.X
	Mean	XX.X
	Median	XX.X
fuer sine u suis	SD	XX.X
lf yes, size y-axis	IQR	xx.x - xxx.x
	Min	xx.x
	Max	XXX.X
	Yes - % (n/N)	xx.x (xx/xx)
Tylidanas of access site related manufacturers	No - % (n/N)	xx.x (xx/xx)
Evidence of access site related pseudoaneurysm	Undetermined - %	xx.x (xx/xx)
	(n/N)	
	Mean	XX.X
	Median	XX.X
f vac size v ovis	SD	XX.X
f yes, size x-axis	IQR	XX.X - XXX.X
	Min	XX.X
	Max	XXX.X
	Mean	XX.X
	Median	XX.X
If you gize y evic	SD	XX.X
lf yes, size y-axis	IQR	xx.x - xxx.x
	Min	XX.X
	Max	XXX.X

Table 20. Follow-up examination of the puncture site

		1 Month	3 Month
Any sign of infantion (viewal)	Yes - % (n/N)	xx.x (xx/xx)	xx.x (xx/xx)
Any sign of infection (visual)	No - % (n/N)	xx.x (xx/xx)	xx.x (xx/xx)
Any palpable	Yes - % (n/N)	xx.x (xx/xx)	xx.x (xx/xx)
inguinal/haematoma mass	No - % (n/N)	xx.x (xx/xx)	xx.x (xx/xx)
present			
	N	XX	xx
	Mean	XX.X	XX.X
	Median	XX.X	XX.X
If yes, measure longest axis (cm)	SD	XX.X	XX.X
	IQR	XX.X - XXX.X	xx.x - xxx.x
	Min	XX.X	XX.X
	Max	XXX.X	XXX.X
Any	Yes - % (n/N)	xx.x (xx/xx)	xx.x (xx/xx)
tenderness/redness/discoloration	No - % (n/N)	xx.x (xx/xx)	xx.x (xx/xx)

Table 21. Medication

	% (n/N)
Heparin	xx.x (xx/xx)
Bivalirudin	xx.x (xx/xx)
Warfarin	xx.x (xx/xx)
Dextran	xx.x (xx/xx)
Aspirin	xx.x (xx/xx)
Ticlopidine	xx.x (xx/xx)
Clopidogrel	xx.x (xx/xx)
Dipyridamole	xx.x (xx/xx)
Abciximab	xx.x (xx/xx)
Tirofiban	xx.x (xx/xx)
Eptifibatide	xx.x (xx/xx)
Other	xx.x (xx/xx)

Table 22. Adverse events / complications summary (CRF data)

	n	
Subjects with non-serious adverse events		
Up to and including haemostasis procedure	xx	
Up to and including discharge	xx	
Up to and including 1 month	xx	
Up to and including 3 month	xx	
Subjects with serious adverse events		
Up to and including haemostasis procedure	xx	
Up to and including discharge	xx	
Up to and including 1 month	xx	
Up to and including 3 month	xx	
Deaths		
Up to and including haemostasis procedure	xx	
Up to and including pre-discharge	xx	
Up to and including 1 month	xx	
Up to and including 3 month	XX	

Table 23. Protocol deviations summary

	Total number of	% (n/N) of subjects
	deviations	with deviations
Subject did not sign informed consent/	XX	xx.x (xx/xx)
inadequate consent process		
Subject did not meet inclusion/exclusion criteria	xx	xx.x (xx/xx)
Follow-up/assessment not completed		
Baseline	XX	xx.x (xx/xx)
Procedure	XX	xx.x (xx/xx)
Discharge	XX	xx.x (xx/xx)
1 month	XX	xx.x (xx/xx)
3 month	XX	xx.x (xx/xx)
Follow-up/assessment not performed according to		
the protocol		
Baseline	XX	xx.x (xx/xx)
Procedure	XX	xx.x (xx/xx)
Discharge	XX	xx.x (xx/xx)
1 month	XX	xx.x (xx/xx)
3 month	XX	xx.x (xx/xx)
Follow-up/assessment out of window		
Baseline	XX	xx.x (xx/xx)
Procedure	XX	xx.x (xx/xx)
1 month	XX	xx.x (xx/xx)
3 month	XX	xx.x (xx/xx)
AE/SAE reporting		
Procedure	XX	xx.x (xx/xx)
Discharge	XX	xx.x (xx/xx)
1 month	XX	xx.x (xx/xx)
3 month	XX	xx.x (xx/xx)
Other		
Baseline	XX	xx.x (xx/xx)
Procedure	XX	xx.x (xx/xx)
Discharge	XX	xx.x (xx/xx)
1 month	xx	xx.x (xx/xx)
3 month	XX	xx.x (xx/xx)

Table 24. Summary of major vascular access site complication types up to 1 months

	subjects with
	complication
Access site related major vascular complications leading to death, life-	XX
threatening (BARC type 5) or major bleeding (BARC type 3a), visceral	
ischemia or neurological impairment	
Distal embolization from the vascular access site requiring surgery or resulting	xx
in amputation or irreversible end-organ damage	
The use of unplanned endovascular or surgical intervention associated with	xx
access site related death, major bleeding (BARC type 3a), visceral ischemia	
or neurological impairment	
Any access site related new ipsilateral lower extremity ischemia documented	xx
by patient symptoms, physical exam, and/or decreased or absent blood flow	
on lower extremity angiogram	
Surgery for access site-related nerve injury	xx
Permanent access site-related nerve injury	xx
Access-site-related infection requiring intravenous antibiotics and/or extended	xx
hospitalization	
Other	xx

Table 25. Summary of minor vascular access site complication types up to 3 months

	subjects	with
	complication	
Access site or access-related vascular injury	XX	
Dissection	XX	
Stenosis	XX	
Perforation	XX	
Rupture	XX	
Arteriovenous fistula	XX	
Pseudoaneurysm (> 3 cm)	XX	
Hematoma (> 6 cm)	XX	
Percutaneous closure device failure	XX	
Distal embolization from the vascular access site treated with	XX	
embolectomy and/or thrombectomy and not resulting in amputation or		
irreversible end-organ damage		
Localized access site infection treated with intramuscular or oral	XX	
antibiotics		
Any access site related unplanned endovascular stenting or unplanned	XX	
surgical intervention not meeting the criteria for a major vascular		
complication		
Access site related vascular repair or the need for vascular repair (via	XX	
surgery, ultrasound-guided compression, transcatheter embolization,		
or stent graft)		
Failure of a closure device to achieve haemostasis at the arteriotomy	xx	
site leading to alternative treatment (other than manual compression or		
adjunctive endovascular ballooning)		
Other ^e	xx	

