11.3 Statistical methods

For continuous variables, the mean, median, standard deviation, interquartile range and minimum-maximum value will be presented. In order to compare subgroups, the differences in means of the subgroups will be tested with a two-sample t-test (in case of 2 subgroups) or with one-way ANOVA (in case of >2 subgroups) in case the assumptions for the required tests are valid. If these assumptions are violated, testing will be done using independent samples Mann-Whitney U tests or Kruskal-Wallis tests (instead of one-way ANOVA).

For categorical variables counts and percentages will be presented. In order to compare differences between subgroups, categorical variables with an expected cell count of at least 5 in 80% of the cells (but no zero expected cell counts) will be tested using the Pearson chi-square test. For categorical variables that do not have an expected cell count of at least 5 in 80% of the cells (or that do have at least one zero expected cell count) and require the differences between the two treatment groups to be tested, the following will be done: Fisher's exact test will be performed for 2x2 contingency tables or the likelihood ratio test will be performed for larger contingency tables.

The tests for all subgroup comparisons assume a significance level of 0.05. No adjustment for multiple testing will be done for any of these variables, as these do not consider the primary endpoint.

Specification for the test concerning the primary endpoint can be found in Section 11.6.

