15. OVERVIEW OF FIGURES TO BE GENERATED

16. TABLES, LISTS AND FIGURES SHELLS

This section will give the format and structure of all tables, lists and figures to be produced in the final Clinical Study Report (CSR).

These detailed specifications can undergo minor revisions during the production phase without needing to revise the SAP. Minor revisions are defined as revisions that do not invalidate any of the specifications in Section 11

16.1 **Tables to be generated**

Table 1. Enrollment summary

Centre	Procedure	No.	No. of	Males/Females	Mean	No. 1	No. 3
		Subjects	closures		Age	month	month
		Enrolled				FU	FU
F4-1	TAVI	XX	XX	xx/xx	XX.X	XX	XX
F4-1	EVAR	XX	XX	xx/xx	XX.X	xx	XX
F4-1	TEVAR	XX	XX	xx/xx	xx.x	XX	XX
F4-1	Other	XX	XX	xx/xx	xx.x	XX	XX

Table 2. Primary endpoint

	% (n/N)	
Major device related	xx.x (xx/xx)	
vascular access site		
complications up to 1		
months		

Table 3. Primary endpoint subgroup comparisons¹

% (n/N)	p-value
 	 

¹ This table will be omitted in the case of low major complication rates and a note will be made of this in the report.

Confidential & proprietary information, not to be reproduced or made available to third parties without prior consent from Vivasure Medical Ltd and not to be used in any unauthorised way.

Major device related

complications up to 1 months

 Centre 1
 xx.x (xx/xx)

 Centre 2
 xx.x (xx/xx)

. . .

Centre x xx.x (xx/xx) x.xxx

Major device related

complications up to 1 months

 TAVI
 xx.x (xx/xx)

 EVAR
 xx.x (xx/xx)

 TEVAR
 xx.x (xx/xx)

Other xx.x (xx/xx) x.xxx

Major device related

complications up to 1 months

Male gender xx.x (xx/xx)

Female gender xx.x (xx/xx) x.xxx

Major device related

complications up to 1 months

 $BMI \le 30 \text{ kg} \qquad \qquad xx.x (xx/xx)$

BMI > 30 kg xx.x(xx/xx) x.xxx

Major device related

complications up to 1 months

No hypertension xx.x (xx/xx)

Hypertension xx.x (xx/xx) x.xxx

Major device related

complications up to 1 months

No diabetes xx.x (xx/xx)

Diabetes xx.x (xx/xx) x.xxx

Major device related

complications up to 1 months

No severe acute non-cardiac xx.x (xx/xx)

systemic disease,

autoimmune disease or

terminal illness

Severe acute non-cardiac xx.x (xx/xx) x.xxx

systemic disease,

autoimmune disease or

terminal illness

Major device related

complications up to 1 months

No bleeding diatheses xx.x (xx/xx)

Bleeding diatheses xx.x (xx/xx) x.xxx

Major device related

complications up to 1 months

No peripheral vascular xx.x (xx/xx)

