disease

Peripheral vascular disease xx.x (xx/xx) x.xxx

Major device related

complications up to 1 months

No previous peripheral xx.x (xx/xx)

vascular surgery involving the

aorta or lower extremities

Previous peripheral vascular xx.x (xx/xx) x.xxx

surgery involving the aorta or

lower extremities

Major device related

complications up to 1 months

No claudication xx.x (xx/xx)

Claudication xx.x (xx/xx) x.xxx

Major device related

complications up to 1 months

No previous arterial access xx.x (xx/xx)

procedure using proposed

artery

Previous arterial access procedure using proposed artery	xx.x (xx/xx)	x.xxx
Major device related complications up to 1 months		
Largest procedural sheath size used ≤ 18 F	xx.x (xx/xx)	
Largest procedural sheath size used > 18 F CFA size?	xx.x (xx/xx)	x.xxx
Age		
Age at procedure ≤ 77	xx.x (xx/xx)	
Age at procedure > 77	xx.x (xx/xx)	x.xxx
Major device related complications up to 1 months		
Sheath size to femoral artery diameter ratio ≤ 1.05	xx.x (xx/xx)	
Sheath size to femoral artery diameter ratio > 1.05	xx.x (xx/xx)	x.xxx
Major device related		
complications up to 1 months		
ACT level at surgery ≤ 160 s	xx.x (xx/xx)	
ACT level at surgery > 160 s	xx.x (xx/xx)	X.XXX

Table 4. Secondary endpoints

	% (n/N)
Minor device related vascular access site	xx.x (xx/xx)
complications up to 1 months	
Technical success rate	xx.x (xx/xx)

Table 5. Compliance to eligibility criteria

	% (n/N)
Patients with 100% compliance to eligibility criteria	xx.x (xx/xx)
Inclusion criteria	Yes: % (n/N)
Patient is over 18 years of age	xx.x (xx/xx)
Patient signed informed consent	xx.x (xx/xx)
Patient indicated for an endovascular procedure using a common femoral arteriotomy created by a 12 – 20 F sheath.	xx.x (xx/xx)
Exclusion criteria	No: % (n/N)
Severe acute non-cardiac systemic disease or terminal illness with a life	xx.x (xx/xx)
expectancy of less than six months	
Evidence of systemic bacterial or cutaneous infection, including groin infection	xx.x (xx/xx)
Known bleeding diathesis, definite or potential coagulopathy, platelet count $<$	xx.x (xx/xx)
$100,\!000/\!\mu I$ or patients on long term anticoagulants with an INR greater than 1.2	
at time of procedure or known type II heparin-induced thrombocytopenia	
Severe; claudication or peripheral vascular disease (e.g. Rutherford category ${\bf 3}$	xx.x (xx/xx)
or greater or ABI < 0.5), documented untreated iliac artery diameter stenosis $>$	

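### SAP Table 3 tests age, BMI, ACT and sheath measures only after cutting each in two; with about four events Fisher's test has little power, and an undefined low rate lets the table be dropped

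*SAP*

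**What the plan says.** SAP 11.5 names age, weight or BMI, ACT, sheath size and common femoral artery diameter among the potential influencing variables. Tables 6, 8, 10 and 11 summarise these measures, or their components, on their original scales. Table 3 in SAP 16.1, the shell that relates them to the primary endpoint, cuts them: "Age at procedure ≤ 77", "ACT level at surgery ≤ 160 s", BMI at 30, largest sheath at 18 F, sheath-to-artery ratio at 1.05. Each pair of groups gets a p-value. Artery diameter appears only as an unfinished entry ending in a question mark.

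SAP 11.3 reserves the Pearson chi-square test for "categorical variables with an expected cell count of at least 5 in 80% of the cells". Otherwise, "Fisher's exact test will be performed for 2x2 contingency tables". On error control it says: "The tests for all subgroup comparisons assume a significance level of 0.05", and "No adjustment for multiple testing will be done for any of these variables". SAP 11.3 also provides the Mann-Whitney test for continuous variables, but the Table 3 shell does not use it. A footnote to Table 3 adds: "This table will be omitted in the case of low major complication rates and a note will be made of this in the report". It gives no threshold for a low rate.

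**The concern.** Cutting a continuous measure in two discards the ordering within each half. With very few events that ordering holds most of the information. The plan expects about four. A real gradient of complications with ACT or age could then easily go undetected, and a non-significant p-value could be read as no influence.

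The footnote adds a second problem. Because low is undefined, whether the comparison is reported at all would be decided after the complication rate is known.

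**Working it through.** **Inputs.** SAP section 10: assumed rate 5%, 75 patients, non-inferiority limit 0.17, one-sided 0.025, power 90%, minimum 68 closures. SAP 11.3: level 0.05; sides are not stated, so two-sided is assumed. No document says how patients divide at any cut.

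**The plan's own figure.** The plan gives no power or event count for Table 3. Its only related figure is the 68 closures. The arcsine formula gives [(1.960 + 1.282) / (2(arcsin√0.17 − arcsin√0.05))]² = 66.02, so 67, close to 68. Then 68 × 1.1 = 74.8, so 75.

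**Expected events.** 75 × 0.05 = 3.75. Under Binomial(75, 0.05), P(4 or fewer) = 0.68 and P(5 or more) = 0.32.

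**Which test applies.** With 4 events at 37/38, the expected event cells are 4 × 37/75 = 1.97 and 4 × 38/75 = 2.03. Only two of four cells reach 5, so Fisher's test is used. Chi-square would need about 11 events (11 × 37/75 = 5.4).

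**Smallest attainable Fisher p-values.** If all events fall in the smaller group of size m, the near tail is C(m, events)/C(75, events). In the rows below the opposite extreme is more probable, so it does not enter and this is the two-sided p.

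| Events | Split | All in smaller group | All in larger group |
|---|---|---|---|
| 3 | 37/38 | 7,770/67,525 = 0.115 | 0.24 |
| 3 | 25/50 | 2,300/67,525 = 0.034 | 0.55 |
| 4 | 37/38 | 66,045/1,215,450 = 0.054 | 0.115 |
| 4 | 36/39 | 58,905/1,215,450 = 0.0485 | 0.116 |
| 4 | 25/50 | 12,650/1,215,450 = 0.010 | 0.29 |
| 5 | 37/38 | 435,897/17,259,390 = 0.025 | 0.054 |

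So p<0.05 is impossible at 37/38 with 4 or fewer events. Beyond that it depends on the split, the direction and the event count. For comparison, the smallest two-sided exact Mann-Whitney p with 4 events and no ties is 2/1,215,450 = 0.0000016.

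**Power.** Simulation of 20,000 data sets: event count drawn from Binomial(75, 0.05), normal covariate, event patients shifted up by 1 SD, two-sided 0.05.

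| Patients above the cut | Fisher power |
|---|---|
| 15 | 27% |
| 25 | 27% |
| 36 | 19% |
| 37 | 11% |
| 38 | 5% |
| 50 | 1% |
| 60 | 0% |

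The exact rank test on the uncut values has about 40% power (37–42% across separate sets of runs). An extreme cut with only 10 patients above it gives Fisher about 30%. A downward shift reverses the order of the table.

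**Ties.** Sheath size takes few values. With an assumed distribution of 8/15/15/37 patients over four sizes, 4 events all at the largest size give an exact rank p of 0.082, against 0.054 for Fisher with those 37 as one group. With 10/20/25/20 the rank p is 0.006, against 0.004 for Fisher at 20/55. A rank test may gain nothing for this variable.

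**The case against.** The strongest reply is that the 37/38 split is the least favourable case and the contrast there turns on one patient. With exactly 4 events and a 1-SD shift, Fisher's power is 0% with 37 above the cut but 45% with 36 above, against 44% for the rank test. With 3 events and 25 above, it is 34% against 33%. The cuts are fixed values, not medians, and no document states an even split. This stands, and it rules out a general claim that Fisher's test cannot succeed here. It does not rescue the cut tables: a split that suits one event count does not suit the next, the favourable cases need the events in the smaller group, and averaged over event counts the rank test was ahead at every cut tried.

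A reader might infer that non-significance is guaranteed by construction. It is not. Five or more events have probability 32%, and 5 events at 37/38 can give p = 0.025. A reader might also infer that the table must vanish whenever the trial succeeds. With 75 patients the exact one-sided 97.5% upper bound is 0.166 at 6 events and 0.183 at 7, so the trial can meet the 0.17 limit with 5 or 6 events, and the footnote does not say whether that counts as low.

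Three further replies have weight. Declining to test on very few events is defensible, and the report would say that the table was omitted. List 6 gives adjudicated complications by subject, and List 7 gives age, BMI and largest sheath size by subject, so some event patients' values could be linked anyway; ACT and artery diameter are not in List 7. SAP section 6 also allows exploratory analyses. What remains is that nothing commits the sponsor to the better comparison, and the omission rule has no threshold.

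**Conclusion.** The point holds as a cheap improvement to an exploratory analysis. At the plan's own rate, Fisher's test on the cut variables has about 0–27% power for a 1-SD shift when between a fifth and four-fifths of patients lie above the cut, against roughly 40% for an exact rank test on data already collected. This rests on normal values, an upward shift, two-sided testing and a true 5% rate. The impossibility of p<0.05 is confined to a 37/38 split with 4 or fewer events. The advantage does not extend reliably to sheath size.

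The undefined low rate is a separate gap that needs no arithmetic. A reader might take either matter to threaten the primary result. It does not: SAP 11.3 places these comparisons outside the primary endpoint test.

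**What to change.** - For age, BMI, ACT, common femoral artery diameter and sheath-to-artery ratio, compare patients with and without a major complication by an exact Mann-Whitney test on the uncut values. This also completes the unfinished artery-diameter entry.
- For largest sheath size, use an exact version that handles ties, and expect little gain.
- Keep the cut tables as n/N only, without p-values.
- List event patients' individual values at any event count, including ACT and artery diameter.
- Delete the footnote, or define low as an event count before any data are seen.
- State that a non-significant result is not evidence of no influence.

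The cost is SAP wording and programming, with no new data and a test already named in SAP 11.3. The tests remain exploratory and unadjusted. Power stays modest: with 4 events the rank test has 44% for a 1-SD shift and 77% for 1.5 SD.
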